C.7. Plasmin and its pro-inflammatory effects: Tranexamic acid is a lysine analogue that interferes with binding of plasminogen to fibrin, which is required for plasmin activation.⁴² Plasmin has pro-inflammatory effects by activating monocytes, neutrophils, platelets, endothelial and dendritic cells and induces pro-inflammatory genes.^{51,52} Plasmin also induces chemotaxis of monocytes and dendritic cells and in-vitro and in-vivo studies have demonstrated the ability of plasmin to stimulate the production reactive oxygen species and promote the release of lipid mediators and cytokines via complement activation.^{51,53} Tranexamic acid benefits in cardiac surgery have been hypothesized to be secondary to a reduction in the inflammatory response, possibly via a reduction of plasmin activation.⁵³⁻⁵⁵ The mortality benefit associated with tranexamic acid may occur secondary to an anti-inflammatory effect due to a reduction in plasmin activation. (Fig 4.)

C.8. Safety and dosing of tranexamic acid: Tranexamic acid has been most commonly used in cardiac surgery and orthopedic surgery for its blood transfusion reduction effects with the risks of thrombotic complications and post-operative seizures being the most common complications reported with its use.^{49,50,56,57} It has been retrospectively compared to other anti-fibrinolytics used in cardiac surgery and shown to have a similar or better safety profile in most studies. Post-operative seizures, due to a GABA receptor antagonist effect, have also been documented following cardiac surgery and this complication is thought to be a dose dependent effect.^{58,59} An orthopedic meta-analysis demonstrated no higher risk of venous thromboembolism following hip and knee replacement, surgeries typically thought to be at increased risk of thromboembolism.⁴⁹ The literature does suggest that further higher level studies are

[figure not shown]

Fig 4. Pro-inflammatory and coagulation system effects of plasmin. Levy JH. *Lancet*. 2010 Jul 3;376(9734):3-4

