required to verify the safety profile of lysine analogue anti-fibrinolytics in the non-injured patient population.^{49,60} The CRASH-2 trial, which looked at over 20,000 patients demonstrated no differences in deaths from vascular occlusive events including myocardial infarction, stroke, and pulmonary embolism and concluded the tranexamic acid safely reduced the risk of death in bleeding trauma patients.⁴¹ Importantly, the trial demonstrated that mortality due to bleeding was increased in patients who received tranexamic acid beyond 3 hours from injury.⁴³ In the retrospective military study (MATTERs, 896 patients) an increased incidence of deep vein thrombosis and pulmonary thromboembolism was demonstrated. These results were, however, confounded by higher injury severity in the tranexamic acid group.⁴⁶

The dosages used in the trauma population studies have been 1 to 2 grams either in loading and/or infusion route, all within the first 8 hours from injury. For the CRASH-2 trial, the dosage regimen was selected to provide a fixed dose within the range shown to inhibit fibrinolysis in larger patients and safe in smaller patients (10 mg/kg loading and 1mg/kg/hr infusion dose).⁴¹ For the military MATTERs study, 1 gram of tranexamic acid was given as a loading dose with the potential for repeat loading dosages.⁴⁶ Based upon these prior studies, the most safe and optimal dosing regimen in trauma patients at risk for bleeding remains obscure.⁶⁰

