P.1. Data Safety Monitoring Board (DSMB): Data safety and monitoring over the course of the clinical trial will fall under the responsibility of an independent data safety and monitoring board. The DSMB will consist of at a minimum, a hematologist with expertise in transfusion medicine, a trauma/critical care surgeon, an epidemiologist with expertise in clinical trial design, and a biostatistician all of whom will have no proprietary interest in the outcome of the trial. The responsibilities of the DSMB will fall under several domains. Prior to beginning the accrual of subjects, the DSMB will review the research protocol and identify logistic problems that may pose problems with randomization schemes and distribution of Tranexamic acid. At this early phase,

the DMSB will also review the plans for data and safety monitoring. At the time of interim analyses, the DMSB will aid in identifying problems surrounding patient accrual and randomization, data collection and follow-up. At this time, the DMSB will also perform an assessment of safety through the comparison of adverse events across both study arms. Lastly, it will fall under the domain of the DMSB to establish whether further conduct of the trial is unnecessary due to strong evidence of benefit or futility.

Although the DSMB will make the final decision about the interim monitoring plan, we anticipate that the DSMB will evaluate the rate of adverse events between the treatment and control arms at 6 months and then annually during enrollment. The DSMB will also monitor primary, secondary study outcomes between the treatment and control groups including main effects and a priori subgroups as specified elsewhere in the protocol. The DSMB will advise the investigators if a change in the protocol is warranted based on this interim monitoring.

P.2. Research Monitor

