Further and in relation to interim safety analysis, safety data by study groups labeled as Interventional group (Early using of tranexamic acid) and Control group (Standard of care) will be provided periodically to DSMB. These processed data will provide information on safety outcomes by treatment group, ascertain the consistency between results for primary and secondary outcomes, and inspect the consistency of treatment effects across subgroups. Safety data of the study include serious adverse events regarding frequency, anticipated or unanticipated, individual description for each event and dates. Other data will be provided as well as any additional safety analysis upon DSMB request. Mortality will be reported as an overall in our periodic reports (every 6-9 months depends on accrual rate) to DSMB however we will report mortality individually as treatment A and B at each of the trial two formal interim analyses. Data will be summarized in tables (3-6)

Table 3 Possible Adverse effects

	Center1		Center2		Center3		Center4		Center5		Total	
	A	B	A	B	A	B	A	B	A	B	A	B
Patients numbers												
Transfusion related lung injury n, (%)												
Allergic/anaphylactic reaction												
Circulatory overload												
Infection												
Febrile reaction												
Hemolytic reaction												
!!!												
!!!												
!!!!												

Table 4 Unexpected Adverse Effects

	Center1		Center2		Center3		Center4		Center5		Total	
	A	B	A	B	A	B	A	B	A	B	A	B
Patients numbers												
1. n,(%)												
2.												
3.												
4.												

Table 5 Primary outcomes for patients in the Study

	Center1		Center2		Center3		Center4		Center5		Total	
	A	B	A	B	A	B	A	B	A	B	A	B
Number of Patients												
24 hr Mortality n, (%)												
30 day Mortality n, (%)												

Table 6 Secondary outcomes for patients in the Study

	Center1	Center2	Center3	Center4	Center5	Total
--	---------	---------	---------	---------	---------	-------

	A	B	A	B	A	B	A	B	A	B	A	B
Number of Patients												
Hyperfibrinolysis												
Acute lung injury (%)												
Multiple organ failure (%)												
Nosocomial infection (%)												
Improved shock parameters (%)												
Early resuscitation need (%)												
Transfusion requirements (%)												
Early seizures (%)												
Pulmonary embolism (%)												
Reduce or prevent the early coagulopathy as demonstrated by improving presenting INR (%)												

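### The planned DSMB safety tables pool the three randomised tranexamic acid regimens, and a breakdown by regimen comes only if the DSMB asks for one

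*Combined protocol and SAP*

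**What the plan says.** Sections H.3.1 and H.3.2 give every patient in the tranexamic acid arm 1 g before hospital. They are then randomised to nothing further (abbreviated), a 1 g infusion (standard), or a 1 g bolus plus a 1 g infusion (repeat). The nominal totals are 1, 2 and 3 g, before the renal adjustment in H.3.2.1.

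The planned safety reporting does not follow that second randomisation:

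- Appendix 4, section 4: "safety data by study groups labeled as Interventional group (Early using of tranexamic acid) and Control group (Standard of care) will be provided periodically". Tables 3 to 6 have columns A and B only, including the early seizure and pulmonary embolism rows of Table 6.
- On deaths, the same section says "we will report mortality individually as treatment A and B at each of the trial two formal interim analyses".
- Section P.1 has the DSMB "perform an assessment of safety through the comparison of adverse events across both study arms" and anticipates that "the DSMB will evaluate the rate of adverse events between the treatment and control arms at 6 months and then annually during enrollment".
- Section P.3 reviews adverse events by treatment arm and names no regimen. The DSMB charter lists seizures and pulmonary embolism for monitoring, also without regimen. The subgroups in J.4 do not include it.

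Appendix 4 also says "Other data will be provided as well as any additional safety analysis upon DSMB request", and it includes an "individual description for each event and dates" among the safety data.

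On dose, section C.8 says of seizures after cardiac surgery that "this complication is thought to be a dose dependent effect". It also states: "The dosages used in the trauma population studies have been 1 to 2 grams either in loading and/or infusion route".

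**The concern.** The repeat regimen has the highest total dose, and the protocol's own background gives most reason to watch it for seizures. In every scheduled display its patients are averaged with those on 1 g and 2 g. An excess confined to the top dose would look much smaller than it is, and a dose gradient would not show at all. The DSMB would then have little basis for advising on one regimen separately from tranexamic acid as a whole. Enrolment is under exception from consent, so the DSMB's view during the trial carries particular weight.

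**Working it through.** **Plan's own figure.** Power for two proportions with a two-sided z-test is Φ[(d − z·s0)/s1]. Here d is the difference in rates, s0 = √[p̄(1−p̄)(1/n1+1/n2)] and s1 = √[p1(1−p1)/n1 + p2(1−p2)/n2]. For 497 per arm and 0.10 versus 0.16 (P.4), s0 = 0.02133 and s1 = 0.02125. Then (0.06 − 1.96 × 0.02133)/0.02125 = 0.856, which gives power 0.804. The plan states 80%. The printed boundaries and drift also return total power 0.800 and total alpha 0.050. No stated figure is in dispute.

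**Inputs.** P.4 gives 166, 332 and 497 per arm at the three looks. Stage 2 uses a block of 9 over three regimens (H.5.2), which implies 1:1:1 but does not state it. That gives about 55, 111 and 166 patients per regimen. The documents give no seizure rates, so the rates below are assumptions: 2% on placebo and 6% on 3 g.

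**Dilution if harm is confined to 3 g.** The pooled rate is (2 + 2 + 6)/3 = 3.33%. An excess of 4.0 points appears as 1.33 points, exactly one third, and a risk ratio of 3 appears as 1.67. The test statistic shrinks less, because the pooled group is larger: 3 × √(2/N)/√(3/N + 1/N) = 2.12-fold. If 5% to 20% of the arm never reached stage 2 (assumed), the dilution of the excess is 3/(1 − a), or 3.2- to 3.75-fold.

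**Dilution if harm is graded.** With the excess linear from 0 g, the regimen rates are 3.33%, 4.67% and 6%, pooled 4.67%. The dilution is 4/2.67 = 1.5-fold. Linear from 1 g, the rates are 2%, 4% and 6%, pooled 4%. The dilution is 4/2 = 2-fold.

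**Power at the second look, harm confined to 3 g.**

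- Pooled: s0 = 0.01250, s1 = 0.01249, (0.01333 − 1.96 × 0.01250)/0.01249 = −0.894, power 19%.
- 3 g versus placebo: s0 = 0.01872, s1 = 0.02385, (0.04 − 1.96 × 0.01872)/0.02385 = 0.138, power 56%.

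| Look (per arm) | Pooled, 3 g only | Pooled, linear from 1 g | Pooled, linear from 0 g | 3 g vs placebo, 0.05 | 3 g vs placebo, 0.05/3 |
|---|---|---|---|---|---|
| 166 | 11% | 19% | 27% | 36% | 24% |
| 332 | 19% | 33% | 48% | 56% | 42% |
| 497 | 26% | 46% | 65% | 70% | 57% |

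**Range at 332 per arm, harm confined to 3 g.** Over placebo rates of 1% to 3% and risk ratios of 2 to 5, power runs from 6% to 66% pooled and from 17% to 97.5% for 3 g versus placebo.

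**Small counts.** A 2% rate among 111 patients is about 2 events. Fisher's exact test lowers the 56% and 42% at the second look to 49% and 32%, and the 36% at the first look to 30%.

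**The case against.** The best reply is that the DSMB can get a regimen breakdown whenever it wants one. Appendix 4 promises further safety analyses on request and individual event descriptions. The charter has the DSMB review individual subject data, and P.1 gives it the final say on the interim monitoring plan. The tables are shells with open rows. Clinical outcomes by regimen are already planned for the trial analysis (I.2, J.3). Safety stopping under the charter rests on clinical judgement, so power at 0.05 is only a rough guide to what the DSMB would notice.

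Much of this stands. A reader might infer that the DSMB is never able to see safety by regimen; the on-request clause rules that out. It does not fully close the gap, because the pooled table can hide the signal that would prompt a request. The charter also routes data requests through the chairperson to the principal investigator, so asking mid-trial could itself reveal a dose concern. Event descriptions are not rates by regimen.

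A second reply also stands in part. If harm rises in proportion to dose from 0 g, the pooled comparison (48%) does better than the multiplicity-adjusted comparison for 3 g (42%). The A/B comparison must therefore stay.

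Three other strong readings fail:

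- The protocol does not assert dose dependence in trauma. It reports a suspected effect from cardiac surgery.
- The repeat regimen cannot be said to breach an 8-hour limit. C.5 describes the large civilian trial as enrolling up to 8 hours after injury and then infusing over eight hours, and the standard regimen has the same infusion.
- A total of 3 g is above the 1 to 2 g stated in C.8, but C.8 also says the military study allowed repeat loading, so the text does not show that 3 g is without precedent.

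**Conclusion.** The point holds as a gap in planned reporting. No scheduled DSMB table or stated comparison separates the three randomised regimens, although the protocol's background gives a reason to look at dose. The size depends on the pattern of harm. The absolute excess is cut to one third only if harm is confined to 3 g and stage 2 is 1:1:1; it is diluted 1.5- to 2-fold if harm is linear in dose. A reader might infer a threefold loss of detectability in general. The calculations do not support that: even in the confined case the test statistic falls about 2.1-fold. All seizure rates are assumed. The change is worth making because it is cheap and concerns safety. The gap does not undermine the primary comparison.

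**What to change.** In the unblinded closed-session reports at the two formal interim analyses, prepared by the independent statistician, add columns for the abbreviated, standard and repeat regimens. Do this in Appendix 4 Tables 3 and 4, and in the mortality, seizure and pulmonary embolism rows of Tables 5 and 6, as a supplement to the A/B comparison.

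- Count regimen events from stage 2 assignment. Give a separate column to tranexamic acid patients who had no stage 2 assignment or whose event came before it.
- Leave the blinded six-monthly reports as A/B. Splitting only the tranexamic acid column there would identify placebo, and the charter keeps those reports blinded and ties unscheduled unblinding to a recalculation of alpha.
- Reconcile the named groups in Appendix 4, section 4, with the charter's blinded display.
- State that the independent statistician receives the stage 2 allocation. H.5.2 names only the investigational drug service and the site pharmacies as holders of the sequence.
- Amend P.1 and P.3 to match.

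No formal boundary is added, and no unblinded look beyond the two already planned. The cost is table layout, a data transfer and small counts (about 55 and 111 per regimen at the two looks), with some chance differences for the DSMB to weigh.

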A summary report of the DSMB's findings will be submitted to regulatory agencies. At least one specialized clinician from the Data Safety Monitoring committee will be responsible for monitoring data safety. All related unanticipated problems will be directly handled by study's PIs and reported accordingly. We will also follow Department Of Defense Unique requirements documentation. The University of Pittsburgh and each participating center will have an AE logbook to record and to assure adequate attention for continuous assessment, analysis, and reporting of adverse effects using a standardized report form. The coordinating center will be responsible for all oversight of these risk assessments with monthly evaluations.

P.4. Interim Analyses: In concert with the DSMB, prior to initiation of the trial, the final monitoring plan will be developed to serve as the guide to the DSMB's decision-making process concerning early stopping of the trial. We will recommend interim analyses as 1/3 and 2/3 of patient enrollment. In making the decision to recommend termination of the study, the DSMB shall be guided by several types of information: (i) a formal stopping rule based on the primary analysis (comparison of treatment groups on the in-hospital mortality and 24 hour blood transfusion requirements), (ii) information on safety outcomes by treatment group, (iii) consistency between results for primary and secondary outcomes, and (iv) consistency of treatment effects across subgroups. Formal interim analyses will be performed at 6 months and then annually throughout enrollment. The DSMB will use the results of implementing the stopping rule as a guideline in evaluating the evidence for treatment effects. In making a recommendation to terminate the study, the DSMB will also consider information on safety outcomes, as well as consistency of outcomes for secondary outcomes and consistency of outcomes within important subgroups as described previously. The group sequential method described by O'Brien and

Fleming will be used to develop stopping rules to limit the impact of repeated testing on the probability of a Type I error.⁹⁵

Based on our power analysis, sample sizes of 497 in interventional group and 497 in control group can achieve 80% power to detect a difference of 0.06 between the group proportions of 0.10 and 0.16 at a significance level (alpha) of 0.05 using a two-sided z-test.

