We have proposed two interim analyses in this trial. We have based our testing on group sequential design that dividing patient entry into a fixed number of equal-sized groups and provides ethical and practical ways to make decision to stop the trial or continue based on repeated significance tests of the accumulated data after each group is evaluated.

According to the above power calculation and following the group sequential method described by O’Brien and Fleming in developing stopping rules to limit the impact of repeated testing on the probability of a Type I error, we will have equally spaced looks at 33%, 67% and 100% of patient accruals. This is equal to 166, 332, and 497 subjects in each group at these three looks. The following table and graph provide in details information in relation to alpha spending functions to determine the test boundaries according to O’Brien-Fleming method.

Details when Spending = O'Brien-Fleming, N1 = 497, N2 =497, P1 = 0.10, P2 = 0.16

Look	Time	Lower Bndry	Upper Bndry	Nominal Alpha	Inc Alpha	Total Alpha	Inc Power	Total Power
1	0.33	-3.71030	3.71030	0.000207	0.000207	0.000207	0.018687	0.018687
2	0.67	-2.51142	2.51142	0.012025	0.011890	0.012097	0.399207	0.417894
3	1.00	-1.99302	1.99302	0.046259	0.037903	0.050000	0.382494	0.800388
Drift 2.82089								

Look: These are the sequence numbers of the interim tests.

Time: These are the time points at which the interim tests are conducted. This is also related to proportion of subject accruals

Lower and Upper Boundary: These are the test boundaries. If the computed value of the test statistic z is between these values, the trial should continue. Otherwise, the trial can be stopped.

[figure not shown]
Nominal Alpha: This is the value of alpha for these boundaries if they were used for a single, standalone test. Hence, this is the significance level that must be found for this look in a standard statistical package that does not adjust for multiple looks.

Inc Alpha: This is the amount of alpha that is *spent* by this interim test. It is close to, but not equal to, the value of alpha that would be achieved if only a single test was conducted. The difference is due to the correction that must be made for multiple tests.

Total Alpha: This is the total amount of alpha that is used up to and including the current test.

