- Trial name: Study of Tranexamic acid during Air and ground Medical Prehospital transport (STAAMP) trial
- Principal investigator (PI): [name], MPH
- Funding agency: Department of Defense
- Trial design: Multi-center, prospective, randomized, blinded, controlled interventional trial.
- Phase: III
- Number of patients: 994
- Number of sites: 4

DSMB Description

- This DSMB will be coordinated by the PI, [name], MPH.
- This DSMB will be independent of the investigators, funding agency, regulatory agencies, and institutional review boards.
- This charter will be approved by its DSMB members as attested to by signature of the chairperson.

DSMB Membership

- Members will disclose conflicts of interest and will be cleared of significant conflicts of interest and potential conflicts of interest in accordance with provisions in this charter.
- DSMB members will sign confidentiality agreements covering DSMB activities.
- Composition of membership will be researchers with the following expertise: hematology (transfusion medicine), surgery (trauma/critical care), prehospital emergency medicine, epidemiology (clinical trial design), and biostatistician.
- Remuneration will be provided any expenses related to DSMB activities.

Reporting

- Unblinded data to be reviewed by the DSMB will be provided by an independent statistician. Issues and recommendations identified by the DSMB will be provided to the principal investigator by the DSMB chairperson in accordance with this charter.
- Details of closed session deliberations (e.g., minutes) will be considered privileged and not subject to disclosure except as required by law.

Introduction

The purpose of this charter is to define the roles and responsibilities of the DSMB, delineate qualifications of the membership, describe the purpose and timing of meetings, provide the procedures for ensuring confidentiality and proper communication, and outline the content of the reports.

The DSMB will function in accordance with the principles of the following documents: FDA document "Guidance for Clinical Trial Sponsors: On the Establishment and Operation of Clinical Trial Data Monitoring Committees".

Study Overview/Summary

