An initial meeting of the DSMB will be held prior to any subject enrollment in the study in order for the members to review the charter, to form an understanding of the protocol and definitions being used, to establish a meeting schedule, and to review the study modification and/or termination guidelines. Subsequent interim and final review meetings will be held to review and discuss interim and final study data (adverse events, protocol deviations, enrollment summary and tables for overall primary and secondary endpoints). Frequency of meetings will be every six months, unless the board determines otherwise.

Meeting Format

DSMB meetings will generally be conducted by teleconference and coordinated by the PI. A quorum, defined as 2 out of 4 members will be required to hold a DSMB meeting. Critical decisions of the DSMB should be made by unanimous vote. However, if this is not possible, majority vote will decide.

Open and Closed Sessions

The open session may be attended by the PI and study investigators or their designees. Data presented in the open session may include enrollment data, individual adverse event data, baseline characteristics, overall data accuracy and compliance data or issues, and other administrative data. Minutes of the open session will be recorded by the Chair of the DSMB. Minutes will be finalized upon signature of the chairperson and maintained by the DSMB in accordance with applicable statutory regulation.

The closed session will be restricted to the DSMB members. A facilitator or recorder may be requested by the DSMB. Data which may compromise the integrity of the study (e.g., comparative

data) will be analyzed and discussed only in the closed session. The minutes of the closed session will be recorded by the DSMB Chair. Minutes from the closed session will be recorded separately from the minutes of the open session and stored securely by the DSMB Chair. Closed session minutes, finalized by signature of the chairperson, will be maintained in confidence and retained until discarded in accordance with applicable statutory regulation.

Following each meeting, a report separate from the minutes of the open and closed sessions will be sent to the PI describing the DSMB recommendations and rationale for such (see DSMB Communication of Findings and Recommendations).

Study Review Criteria/Stopping Rules and Guidelines

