Guidance for the conduct of safety and efficacy analyses, and guidelines / stopping rules will be established prior to the DSMB's first evaluation of data.

Safety Analyses

The primary safety endpoint is mortality as observed during interim analysis. In addition to the primary safety endpoint, the DSMB will monitor the following adverse events:

1. Acute Lung Injury
2. Nosocomial infection
3. MOF (multiple organ failure)
4. Early seizures
5. In-hospital pulmonary embolism
6. Blood and blood component transfusion and resuscitation requirements
7. Adverse Events
8. Unexpected Adverse Events
9. Expected Adverse Events

Stopping Guidelines / Stopping Rules: Safety

Termination or modification may be recommended for any perceived safety concern based on clinical judgment, including but not limited to a higher than anticipated rate for any component of the primary endpoint resulting in adverse events, or unexpected SAEs.

Efficacy Analyses

The primary outcome variable 30 day mortality will be utilized to assess for efficacy of the trial. Accessing this primary outcome variable at each interim analysis will allow early termination of the trial for either lack of efficacy or excessive efficacy.

Adaptive Protocol Modification

There is no planned sample size re-estimation; however if the DSMB reveals a need, the sample size calculation can be re-evaluated.

Consideration of External Data

The DSMB will also consider data from other studies or external sources during its deliberations, if available, as these results may have a profound impact on the status of the patients and design of the current study.

DSMB Reports

Monitoring for Safety

The primary charge of the DSMB is to monitor the study for patient safety. Formal DSMB safety reviews will occur as specified above (see Study Review Criteria/Stopping Rules and Guidelines).

Monitoring for Efficacy

The DSMB will monitor efficacy outcomes to determine relative risk/benefit, futility, or for early termination due to overwhelming efficacy. Interim analyses efficacy reports sent to the DSMB will occur as specified above (see Study Review Criteria/Stopping Rules and Guidelines).

Monitoring for Study Conduct

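### Appendix 4 and the DSMB charter conflict on whether the board sees mortality by arm between the two formal looks

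*Combined protocol and SAP*

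**What the plan says.** **Appendix 4, section 4 (Monitoring Safety and efficacy).** Safety data go to the DSMB periodically under named study groups. These data are meant to "ascertain the consistency between results for primary and secondary outcomes, and inspect the consistency of treatment effects across subgroups". The same paragraph then says: "Mortality will be reported as an overall in our periodic reports (every 6-9 months depends on accrual rate) to DSMB". It adds that mortality is split into treatments A and B at each of the two formal interim analyses. It also lets the DSMB request further safety analyses, and its Table 5 shell has A and B columns for 24-hour and 30-day mortality.

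**DSMB charter (Appendix 3).**
- Projected Schedule of Meetings: "Frequency of meetings will be every six months, unless the board determines otherwise".
- Preparation of Reports to the DSMB: at these meetings the closed session sees outcomes by treatment with the arms still coded. If the results are worrying, the board reconvenes within a week to see the same data unblinded. That session counts as an added interim analysis, with alpha recalculated.
- Safety Analyses: "The primary safety endpoint is mortality as observed during interim analysis".

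**Protocol.**
- P.1 expects adverse-event rates to be compared between arms at 6 months and then annually. It adds, without an interval: "The DSMB will also monitor primary, secondary study outcomes between the treatment and control groups including main effects and a priori subgroups".
- P.4 recommends interim analyses at 1/3 and 2/3 of enrolment, but also schedules formal interim analyses at 6 months and then annually.

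**The concern.** Mortality is both the primary outcome and the charter's primary safety endpoint. Under Appendix 4 the board would weigh emboli, seizures and organ failure by arm between looks without knowing which arm had more deaths. A raised pooled rate could mean a harmful arm or a sicker population. Enrolment is under exception from consent, and the background (C.8) itself cites higher bleeding mortality with late tranexamic acid and more thromboembolism in a retrospective military cohort.

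Under the charter the board would see coded outcomes by arm every six months. The statistician preparing the closed-session report therefore has two opposite instructions on the most important safety variable. The report interval also varies: 6 to 9 months in Appendix 4, six months in the charter, and 6 months then annually in P.1.

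**Working it through.** **1. The plan's own figures.** The charter gives "Number of patients: 994" and P.4 says "This is equal to 166, 332, and 497 subjects in each group at these three looks". One third of 994 is 331.3, or about 166 per group; two thirds is 662.7, or 331 to 332 per group. With O'Brien-Fleming-type spending, 4[1 − Φ(z/√t)] where z is the 1 − 0.05/4 normal quantile, at t = 1/3, 2/3 and 1:
- cumulative alpha is 0.000207, 0.012097 and 0.050000;
- boundaries are 3.7103, 2.5114 and 1.9930;
- cumulative power at the stated drift of 2.82089 is 0.0187, 0.4179 and 0.8004.

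All agree with the printed table. The two-look design is sound, and the point concerns only what is shown between looks.

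**2. Accrual inputs.** Section F gives 33 months of enrolment and about 70 patients per centre per year. Section A gives 330 in year 1. K.1 gives 80 per centre per year. The charter gives 4 sites. Appendix 4, section 1, puts each look about one month after 1/3 and 2/3 accrual.

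**3. Patients enrolled without by-arm mortality if Appendix 4 governs.** Enrolled at a look = fraction × 994 + one month of accrual.

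| Monthly accrual | Enrolled at look 1 (month) | Added by look 2 | Enrolled after look 2 |
|---|---|---|---|
| 994/33 = 30.1 | 331.3 + 30.1 = 361 (12.0) | 331 | 301 |
| 330/12 = 27.5 | 331.3 + 27.5 = 359 (13.0) | 331 | 304 |
| 4 × 80/12 = 26.7 | 331.3 + 26.7 = 358 (13.4) | 331 | 305 |
| 4 × 70/12 = 23.3 | 331.3 + 23.3 = 355 (15.2) | 331 | 308 |

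Taking the looks at 33% and 67%, or at exactly 332 and 664 patients, widens the ranges to 351–362, 331–338 and 298–308.

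**4. If the charter governs.** Coded by-arm outcomes first arrive at month 6, after 6 × 23.3 = 140 to 6 × 30.1 = 181 patients, and every six months after that.

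**5. What a pooled rate hides.** P.4's design rates are 0.10 and 0.16. At look 1, with 166 per group, the expected deaths are 166 × 0.10 = 16.6 and 166 × 0.16 = 26.6. That is 43.2 of 332, or 13.0%. Exchange the arms and the pooled figure is the same 43.2. Put 13% in both arms and it is again 2 × 21.6 = 43.2. Benefit, harm and no effect all give the same overall report.

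**6. Report interval.** At 27.5 per month, intervals of 6, 9 and 12 months mean 165, 248 and 330 patients between reviews.

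**The case against.** A reader might infer that the plan keeps mortality by arm from the board between looks and so makes the consistency check impossible. The documents do not support that as a flat statement:
- The charter's six-monthly closed session shows coded outcomes by treatment and has an escalation route.
- Appendix 4 allows extra safety analyses on request, by-arm adverse events could prompt one, and P.1 leaves the final monitoring plan to the DSMB.
- Consistency across subgroups can still be examined for outcomes other than death.
- The Appendix 4 paragraph opens by referring to interim safety analysis, so part of it may describe the formal looks.

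Two further inferences also fail. The charter's definition of its primary safety endpoint does not contradict Appendix 4, because it is mortality as seen at the interim analyses. P.1 does not set a six-month or annual comparison of the primary outcome, because that timing belongs to adverse events.

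It can also be argued that how often a board sees deaths by arm is a design choice, and that frequent views invite informal stopping for benefit.

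These points narrow the concern without removing it. The charter's provision is what makes Appendix 4 contradictory. The request route is a weak safeguard, because the charter treats an unscheduled unblinded session as another interim analysis that costs alpha. That deterrent is unnecessary for harm: a review that can stop only for harm cannot raise the chance of falsely declaring benefit, although a mistaken stop would cost power. The risk of informal stopping for benefit is real and can be met by an explicit rule.

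**Conclusion.** The conflict is real and should be resolved. Appendix 4 and the charter disagree on whether mortality is shown by arm between the formal looks, and neither is said to prevail. If Appendix 4 is followed and the board makes no request, the gaps are about 360, 330 and 300 patients. These counts rest on the documents' planned accrual and the one-month lag. If the charter is followed, coded outcomes arrive from month 6 and the gaps do not arise.

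For mortality, the primary-versus-secondary check that Appendix 4 assigns to its periodic data cannot be made from a pooled figure. For other outcomes it is not blocked.

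A reader might go on to count avoidable deaths. That would need an assumed size of harm, which the documents do not give, and certainty that the board would stop at month 6, so no such figure is offered. The two-look alpha calculation is unaffected.

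**What to change.** 1. **Appendix 4, section 4.** Replace the pooled-mortality sentence with: *At every scheduled closed session the independent statistician reports 24-hour and 30-day deaths by coded arm (Table 5) with the other safety data, for harm review only. Efficacy is tested, and alpha spent, only at the 1/3 and 2/3 looks and the final analysis. The trial may not be stopped for benefit at any other review.* Label the arms the same way in all tables: named arms in the adverse-event tables would defeat the coding of deaths.
2. **Charter, Preparation of Reports to the DSMB.** Say that unblinding for a harm-only review is not an added efficacy analysis and does not require alpha to be recalculated.
3. **P.1 and Appendix 4.** State one safety-report interval, the charter's six months.
4. **P.4.** Keep formal interim analyses at 1/3 and 2/3 of enrolment only and remove the calendar schedule for them. Do not make them six-monthly, which would break the two-look design.

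The cost is wording in four places and one closed-session table whose shell already exists. The downside is that the board sees mortality by arm more often, so the bar on stopping for benefit outside the formal looks is an essential part of the change.
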